Statistical Analysis Plan for the study: "The effects of Menaquinone-7 supplementation in patients with severe coronary calcifications: study protocol for a randomized controlled trial"

SAP authors: [name] ^a, [name] ^b, [name] ^a

Affiliations:

^a Open Patient data Explorative Network (OPEN), Odense University Hospital and Department of Clinical Research, University of Southern Denmark, Odense, Denmark

^b Department of Cardiology, Odense University Hospital, Odense, Denmark

Introduction

This document specifies the planned statistical analysis for the study "The effects of Menaquinone-7 supplementation in patients with severe coronary calcifications: study protocol for a randomized controlled trial" as carried out following the protocol published at ClinicalTrials.gov Identifier: NCT05500443.

Sample size considerations

According to the protocol (1): "We are planning a study of a continuous response variable from independent control and experimental subjects with 1 control per experimental subject. In the AVADEC trial, the mean (standard deviation) two-year CAC progression among 182 men with CAC score ≥ 400 was 380 AU (330 AU) in the placebo group and 288 AU (280 AU) in the intervention group. The joint standard deviation was 311 AU. If this is true in a population of men and women, inclusion of 180 experimental subjects and 180 control subjects are needed to be able to reject the null hypothesis that the population means of the experimental and control groups are equal with probability (power) 0.8. The Type I error probability associated with this test of this null hypothesis is 0.05 (two-sided). Accordingly, 360 subjects are needed. However, to comply with the uncertainty and to account for drop-out of 10%, 400 patients will be included. The sample size is based on two years of treatment."

Randomizations

Randomization is performed by the pharmacy at Odense University Hospital. Based on a computergenerated assignment scheme the tablets will have a random number according to the sequential order.

Statistical principles

All analyses were performed in the intention-to-treat population and as superiority analyses. Two-sided p-values of 0.05 or less were considered to indicate statistical significance and associations and effect estimates will be reported with 95% probability symmetric confidence interval (2.5% to 97.5% quantile).

Practical considerations

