Data are collected using REDCap hosted by OPEN (Open Patient data Explorative Network, Odense University Hospital, Odense Denmark) with project number OP_1703. Data are analyzed using Stata on OPEN's secure analysis server (OPEN Analyse). A prespecified random seed of 319846 will be used for bootstrapping and/or imputation if these methods are deemed nescessary.

Planned analyses for primary publication

Outcomes

Primary outcome: Main analysis

The primary outcome is the change in coronary artery calcification (CAC) score (numerical) from baseline to 24 month for the full cohort of included patients.

Secondary outcomes

Secondary outcomes are:

- Change in CAC score from baseline to 24 months in men and women, respectively
- Change in CAC score from baseline to 24 months in two pre-specified subgroups (baseline CAC score <1000 and ≥ 1000)
- Change in coronary plaque composition by contrast CT from baseline to 24 months
- Change in calcifications in the aortic valve by non-contrast CT from baseline to 24 months
- Cardiac events (non-fatal myocardial infarction, coronary revascularization, and cardiac death) during the follow-up period
- Change in quality of life from baseline to 24 months.

An exploratory endpoint is:

• Change in MGP with different phosphorylation (p and dp) and carboxylation forms (c and uc).

Safety outcomes

Safety outcomes are:

- Death
- Cardiovascular events (myocardial infarction, coronary revascularization, heart valve surgery, stroke, significant aortic disease (dissection, rupture and surgery) and significant peripheral artery disease (thromboembolisms and surgery)
- Venous thromboembolism including pulmonary embolism
- Bleeding (including intracranial bleeding and hemorrhage associated with a drop in hemoglobin of
 ≥ 2mmol/I)
- Cancer, including solid and hematologic
- Significant deterioration in laboratory measurements (hemoglobin, creatinine (eGFR), sodium, potassium, calcium, magnesium, albumin, phosphate, alkaline phosphatase, parathyroid hormone or prothrombin time-international normalized ratio (PT-INR)).

Dichotomous safety outcomes are evaluated as occurred / not occurred between baseline and 24 months. Numerical safety outcomes are evaluated as change from baseline to 12 and 24 months.

Planned tables and figures and corresponding analyses

Table 1. Characteristics of patients at baseline

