Primary outcome and numerical secondary outcomes will be analyzed by mixed effects linear regression. The mixed effects linear regression models will include a fixed effect for treatment, a fixed effect for time point (baseline, 12 and 24 months) and a fixed effects interaction between treatment and time point. As baseline measurements are obtained before randomization, treatment at baseline will be modelled as a separate common treatment category, constraining baseline measurements to no systematic treatment effect between the two treatment arms, as suggested in literature (6). All mixed effects models will include a random intercept for each included patient. Normality assumptions on residuals and random effects will be evaluated by normal quantile-quantile plots. In case deviations from normality assumptions are detected analyses will be repeated with nonparametric bootstrapping with 1,000 bootstrapping samples (handling individual patients as bootstrapping clusters, and treatment groups as bootstrapping strata).

	Vitamin K+D group	Placebo group	Group difference	
	Mean change from	Mean change	Treatment effect	p-value
	baseline (95 % CI)	from baseline	(95 % CI)	
		(95 % CI)		
Primary outcome				
CAC score (all				
patients)				
Numerical secondary of	utcomes			
CAC score (men)				
CAC score (women)				
CAC score				
(baseline CAC score				
400-999)				
CAC score				
(baseline CAC score				
≥1000)				
AVC score (all				
patients)				
dp-ucMGP				
Quality of life				

All available data will be used in the analyses in Table 2.

Table 3. Secondary outcome on plaque composition

Analyses on change from baseline to 24 months on per patient level in all participants will be carried out similar to Table 2.

	Vitamin K+D group	Placebo group	Group difference	
	Mean change from	Mean change	Treatment effect (95	p-value
	baseline (95 % CI)	from baseline (95	% CI)	
		% CI)		
Plaque volume and c	composition			
Total plaque (mm ³)				
Calcified plaque				
(mm ³)				
Noncalcified plaque				
(mm ³)				
Low-attenuation				
noncalcified plaque				
(<30 HU) (mm³)				

Table 4. Dichotomous secondary outcome and adverse events

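### Cheap improvement: 1,000 bootstrap samples leave avoidable Monte Carlo error in the primary confidence limits if the fallback is used; 10,000 would largely remove it

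*SAP*

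**What the plan says.** Four parts of the SAP bear on this point.

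- **Table 2, primary and numerical secondary outcomes.** The mixed model is checked with normal quantile-quantile plots. If these show departures from normality, "analyses will be repeated with nonparametric bootstrapping with 1,000 bootstrapping samples", "handling individual patients as bootstrapping clusters, and treatment groups as bootstrapping strata". The section names no bootstrap interval type and no way of obtaining the bootstrap p-value. The table shell has a p-value column beside the treatment effect and its confidence interval.
- **Statistical principles.** Effect estimates in general are reported with a "95% probability symmetric confidence interval (2.5% to 97.5% quantile"). Significance is judged by a two-sided p-value of 0.05 or less.
- **Practical considerations.** "A prespecified random seed of 319846 will be used for bootstrapping and/or imputation", if these methods prove necessary.
- **Sample size considerations.** The planning values are mean two-year progression of 380 AU (SD 330) and 288 AU (SD 280), a joint SD of 311 AU, and 180 patients per arm for power 0.8 at two-sided 0.05.

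**The concern.** A limit read from the 2.5% or 97.5% quantile of 1,000 replicates rests on about 25 replicates in each tail, since 0.025 × 1,000 = 25. That count varies from one set of resamples to another, and so does the limit. Fixing the seed decides which set of resamples is reported. It does not bring that set closer to the answer that very many resamples would give. If the exact bootstrap p-value lies near 0.05, whether the primary interval excludes zero depends partly on the draw and not only on the data.

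A smaller matter goes with it. The SAP does not say where the p-value comes from once the bootstrap is in use. A quantile-based interval paired with a p-value from another route need not give the same answer for a borderline result.

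**Working it through.** **Inputs.** From the SAP: difference 380 − 288 = 92 AU, SD 311 AU, 180 per arm, two-sided alpha 0.05, B = 1,000 bootstrap samples. Assumed: a normal bootstrap distribution, a simple two-group standard error in place of the mixed-model one, and B = 10,000 as the alternative.

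**Step 1. The plan's own figure.** n per arm = 2 × (1.960 + 0.842)² × 311² / 92² = 179.4, so 180. The total is 360, and 360 / 0.9 = 400. The sample size reproduces, with power 0.801 at 180 per arm.

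**Step 2. Scale.** SE of the difference = 311 × √(2/180) = 32.8 AU. Half-width of the 95% interval = 1.96 × 32.8 = 64 AU.

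**Step 3. Monte Carlo error of a percentile limit.** In units of the bootstrap SE it is √(0.025 × 0.975 / B) / φ(1.96), with φ(1.96) = 0.0584.

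- B = 1,000: 0.00494 / 0.0584 = 0.0845 SE; × 32.8 = 2.8 AU, and 2.8 / 64 is about 4% of the half-width.
- B = 10,000: 0.00156 / 0.0584 = 0.0267 SE; × 32.8 = 0.9 AU.

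The matching Monte Carlo SD of a percentile p-value at 0.05 is 2 × √(0.025 × 0.975 / B): 0.0099 at 1,000 samples and 0.0031 at 10,000.

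**Step 4. Chance of a wrong verdict at a given exact bootstrap p.** Let X be the number of replicates beyond zero in the smaller tail, so X is binomial (B, p/2). The interval excludes zero when X is below 0.025 × B.

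| Exact p | B = 1,000 | B = 10,000 |
|---|---|---|
| 0.03 | 1.1% | below 0.1% |
| 0.04 | P(X ≥ 25) = 15.5% | 0.03% |
| 0.045 | 32% | 5% |
| 0.048 | 45% | 27% |
| 0.052 | 39% | 26% |
| 0.06 | P(X ≤ 24) = 15.3% | 0.12% |
| 0.08 | 0.4% | below 0.1% |

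At p exactly 0.05 the verdict is close to a coin toss for any B.

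**Step 5. Averaged over trials.** Weight the Step 4 probabilities by the distribution of the test statistic: normal with SD 1 and mean 92 / 32.8 = 2.81 under the design effect, or mean 0 under the null. This gives the share of trials in which the verdict differs from the exact bootstrap.

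| Limits | B | Design effect | Null |
|---|---|---|---|
| Percentile | 1,000 | 1.9% | 0.8% |
| Percentile | 10,000 | 0.6% | 0.25% |
| Normal-based on bootstrap SE | 1,000 | 1.0% | 0.4% |

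The last row applies if the bootstrap supplies only a standard error. Its relative Monte Carlo error is 1 / √(2 × 999) = 0.0224, which moves a limit by 1.96 × 32.8 × 0.0224 = 1.4 AU.

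**Step 6. Type I error.** With 1,000 samples and percentile limits, the rejection rate under the null is 0.050 or 0.052, depending on whether exactly 25 replicates beyond zero counts as excluding it.

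**The case against.** The case against raising this at all is strong. The SAP fixes the number of samples, the clusters, the strata and the seed, so nothing is stated wrongly. The quantile wording is a general reporting rule, and the bootstrap sentence names no interval type; with normal-based limits the error is about half as large. The bootstrap is conditional and repeats an analysis whose mixed-model result has no Monte Carlo error. Nor does 10,000 samples abolish the borderline zone, as the rows at 0.045, 0.048 and 0.052 show. All of this stands, and it is why the point is an improvement and not an error. What it leaves untouched is that the Monte Carlo error is real, that the seed does not shrink it, and that shrinking it costs almost nothing.

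Four stronger readings are tempting, and the SAP does not support them.

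- **The result can be steered through the seed.** It cannot: the seed is fixed in advance at 319846, and analysts following the plan cannot choose among seeds.
- **The primary conclusion is unreliable in general.** The 15% figures apply only if the exact p-value lands at 0.04 or 0.06. Averaged over trials the discordance is about 2% or less, and type I error stays at about 0.05.
- **The fallback will probably be used.** A normal distribution with the planning means and SDs would put 12% (380/330) and 15% (288/280) of patients below zero. That hints at right skew, but a change score can be negative and the SAP gives no distribution, so likely use is not established.
- **The interval and the p-value will contradict each other.** The SAP specifies no conflicting p-value route. It specifies none for the bootstrap, so the disagreement is hypothetical and supports only a clarifying sentence.

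**Conclusion.** The point holds as a low-cost refinement. If the fallback is triggered and the quantile rule is applied to it, the limits of the primary interval are blurred by about 2.8 AU for a reason unrelated to the data, and in roughly 1 to 2 trials in 100 the verdict would differ from that of an exact bootstrap. That matters only for a result close to 0.05.

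The figures rest on the planning SD and 180 patients per arm, a normal bootstrap distribution and a simple two-group standard error. A different standard error scales the AU figures in proportion. The chance of a wrong verdict at a given exact p under percentile limits does not depend on it.

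**What to change.** In the SAP section on Table 2, replace 1,000 by 10,000 bootstrap samples for the primary outcome. Add one sentence stating that the confidence interval is the 2.5% and 97.5% quantiles of the bootstrap distribution, and that the two-sided p-value is taken from the same distribution as twice the smaller share of replicates beyond zero. The two will then agree apart from the handling of exact ties at the limit. Keep the prespecified seed, the patient clusters and the treatment-group strata as they are.

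The cost is one number, one sentence and computing time: ten times as many fits, each on about 1,200 rows (400 patients × 3 time points). The design, the estimand and the main mixed-model analysis do not change.

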Dichotomous secondary outcomes and adverse events are reported as counts and proportions separately for each treatment group and compared between groups by χ^2 -test if all counts are at least 5, or with Fisher's exact test otherwise. If a patient reported multiple events of the same outcomes, this will be handled dichotomously as experiencing the outcome in the analyses, but the count of such patients will be reported in a parenthesis or footnote to the table.

All available data will be used in the analyses in Table 2, and number of missing observations in each group will be specified.

Event	Vitamin K +D group (N=XX)	Placebo group (N=XX)	p-value
Secondary outcome			
Cardiovascular events (combined) – no (%)			
 Non-fatal myocardial infarction 			
Coronary revascularization			
Cardiac death			
Adverse Events			
Any event – no (%)			
Death – no (%)			
Cardiovascular events (combined) – no (%)			
Myocardial infarction			
Coronary revascularization			
Heart valve surgery			
• Stroke			
 Significant aortic disease (dissection, rupture and surgery) 			
Significant peripheral artery disease			
(thromboembolism and surgery)			
Venous thromboembolism – no (%)			
Severe bleeding – no (%)			
Incident cancer – no (%)			

Table 5. Numerical safety outcomes

Numerical safety outcomes will be analyzed by linear mixed models corresponding to the analyses specified for the primary outcome in Table 2. No subgroup analyses will be performed.

	Vitamin K+D group	Placebo group	Group difference	
	Mean change (95 %	Mean change	Treatment	P-
	CI)	(95 % CI)	effect (95 % CI)	value
hemoglobin				
creatinine (eGFR)				
carbamide				
sodium				
potassium				
calcium				
magnesium				
albumin				
phosphate				
Alkaline phosphotase				
parathyroid hormone				
prothrombin time-				
international				
normalised ratio (PT-				
INR)				

Supplementary Table S1. Stratified analyses of the primary outcome

Analyses of the primary outcome (progression in CAC score) will be repeated stratifying for age (below or above mean age at baseline), diabetes (yes / no at baseline), hypertension (yes / no at baseline), renal failure (yes / no at baseline), statin therapy (yes / no at baseline), and MGP (below / above median). In these analyses, patients will not be stratified by baseline CAC score 400-999 and ≥1000. The same models as for Table 2 will be applied for these analyses.

	Vitamin K +D group	Placebo group		

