Coefficients with 95% confidence intervals from stratified analyses (as reported in Supplementary table 1) for differences in primary outcome (change of CAC score from baseline to 24 months) between treatment groups will be presented as a forest plot. (See mockup figure below.)

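### Table 4 compares clinical events and dichotomous safety outcomes by p-value alone, with no effect estimate or 95% CI

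*SAP*

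**What the plan says.** Under Table 4, the SAP states that "Dichotomous secondary outcomes and adverse events are reported as counts and proportions separately for each treatment group and compared between groups by" a chi-square "test if all counts are at least 5, or with Fisher's exact test otherwise". The shell agrees with the text: one column per arm in n (%) format, then a p-value.

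The rows include the only clinical-event secondary outcome, listed under Secondary outcomes as "Cardiac events (non-fatal myocardial infarction, coronary revascularization, and cardiac death) during the follow-up period", and the dichotomous safety outcomes: death, cardiovascular events, venous thromboembolism, severe bleeding and incident cancer.

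Elsewhere the SAP plans estimates. Statistical principles says that "associations and effect estimates will be reported with 95% probability symmetric confidence interval". For Table 5, "Numerical safety outcomes will be analyzed by linear mixed models corresponding to the analyses specified for the primary outcome in Table 2", and that shell has a treatment-effect column with 95% CI. Figure 4 will plot "Coefficients with 95% confidence intervals from stratified analyses".

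**The concern.** A p-value from a 2x2 table does not say how large a difference the data are compatible with. That matters most where events are few and the trial was not sized for them, which is the position of every row in Table 4. A non-significant result on bleeding, thromboembolism or cardiac events is easily read as absence of harm when the data may be compatible with a substantial excess.

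The SAP fixes an effect measure for every numerical comparison and none for the dichotomous ones. If an estimate is wanted at the reporting stage, both the measure and the interval method will be chosen after the counts are known.

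A smaller point sits in the same sentence. The condition "if all counts are at least 5" reads most naturally as observed counts, whereas the usual condition for the chi-square test concerns expected counts. The effect is to send some tables to the more conservative Fisher test without need.

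**Working it through.** **1. Table shells side by side.**

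| SAP table | Between-group p-value | Treatment effect (95% CI) |
|---|---|---|
| 2, 3, 5, S1, S2 | yes | yes |
| 4 | yes | no |
| 1, S3 | no | no (no between-group comparison) |

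Six tables carry a between-group p-value. Five give an estimate with an interval, and Table 4 is the only exception.

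**2. What the trial is sized for.** Inputs from Sample size considerations: means 380 and 288 AU (difference 92), joint SD 311 AU, two-sided alpha 0.05, power 0.8, allocation 1:1.

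n per arm = 2 × (1.960 + 0.842)² × (311/92)² ≈ 179.4, rounded up to 180. Then 360/0.9 = 400. The stated figures reproduce, with power 80.1% at 180 per arm. No event rate enters the calculation.

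**3. What Table 4 would leave out.** The SAP gives no event rates, so every count below is an assumption, at n = 200 per arm.

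For 16 v 8 events (8% v 4%):
- Chi-square, uncorrected: (16 − 8)² × 400 / (24 × 376) = 2.84, p = 0.092.
- Risk ratio 2.0. SE of the log = √(1/16 − 1/200 + 1/8 − 1/200) = √0.1775 = 0.421. 95% CI = 2.0 × exp(±1.96 × 0.421) = 0.88 to 4.57.
- Newcombe risk difference, from Wilson limits of 4.98% to 12.60% and 2.04% to 7.69%:
  - lower = 4.0 − √((8.00 − 4.98)² + (7.69 − 4.00)²) = −0.8 points
  - upper = 4.0 + √((12.60 − 8.00)² + (4.00 − 2.04)²) = 9.0 points

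At 180 per arm the same counts give p = 0.091, a risk ratio CI of 0.88 to 4.56, and a risk difference of 4.4 points (−0.8 to 10.0).

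Equal counts in the two arms always give p = 1.0, but they exclude very different effects:

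| Events (200 per arm) | p | Risk ratio 95% CI | Risk difference 95% CI (points) |
|---|---|---|---|
| 4 v 4 | 1.0 | 0.25 to 3.94 | ±3.3 |
| 10 v 10 | 1.0 | 0.43 to 2.35 | ±4.6 |
| 20 v 20 | 1.0 | 0.56 to 1.80 | ±6.0 |

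**4. How often the planned test would detect a true doubling of risk.** Exact binomial enumeration at 200 per arm, reading the rule as observed counts: 4% for 1% v 2%, 13% for 2% v 4%, and 47% for 5% v 10%. Under these assumed risks a non-significant result is more likely than not even when the risk truly doubles.

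**5. The test-choice rule.** I enumerated all tables in which the smaller event count is below 5 and the expected event count per arm is at least 5. The two readings differ on nominal significance only at these tables (p-values at 200 per arm):

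| Events | Chi-square p | Fisher p |
|---|---|---|
| 2 v 9 | 0.032 | 0.062 |
| 3 v 10 | 0.048 | 0.087 |
| 3 v 11 | 0.030 | 0.053 |
| 4 v 12 | 0.041 | 0.071 |

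The probability of landing on one of them is 0.5% at 1% v 2%, 6% at 2% v 4%, 10% at 1.5% v 5%, and 0.04% at 5% v 10%. At 2% v 4% the expected-count rule raises the rejection probability from 13% to 20%. With equal risks of 2%, 3% and 5%, type I error is 1.7%, 2.3% and 4.1% under the observed-count rule, and 2.4%, 4.3% and 4.8% under the expected-count rule. Both stay below 5%.

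**The case against.** Nothing in Table 4 is formally wrong. The sentence in Statistical principles can be read as governing only the estimates that are produced, and none is planned here. The other tables come from mixed models, whose natural output is a coefficient with a CI, whereas Table 4 is a set of simple tests. Counts, percentages and denominators will be published, so any reader can compute a risk difference, and a late choice of measure alters neither the counts nor the prespecified p-value. The chances of significance in step 4 are properties of the sample size, and an added interval does not change them. The chi-square wording is a separate matter: Fisher's test is valid, error is controlled under either reading, and with equal risks of 1%, 2%, 3% and 5% the two readings disagree in only about 0.01%, 0.7%, 2.0% and 0.7% of trials.

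Much of this stands. The SAP does not breach its own rule, the primary analysis is untouched, and the test-rule wording is minor. It does not answer the main point. Leaving readers to derive an interval means that the plan fixes neither the measure nor the method, and the paper's own statements about harm would rest on p-values. The low chance of significance is why an interval is needed: it shows what the data cannot exclude.

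**Conclusion.** The point holds as a worthwhile improvement, not as an invalid analysis. For the cardiac-events secondary outcome and all dichotomous safety outcomes, the SAP prespecifies a test and no effect measure or interval, alone among its six comparative tables. How much this hides depends on event counts that the SAP does not give. Under the assumed counts at 200 per arm, p = 0.09 can accompany a risk difference interval reaching 9 points, and p = 1.0 can accompany risk ratio intervals as different as 0.25 to 3.94 and 0.56 to 1.80. The test-choice wording costs a little sensitivity, at most 10% of trials in the unequal-risk scenarios set out above. The sample size, the primary outcome and the numerical analyses are not affected.

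**What to change.** Add one column to Table 4 giving the risk difference with 95% CI by a named method. Newcombe is suitable because it also works when one arm has no events. For the cardiac-events composite, add the risk ratio with 95% CI. State that safety outcomes are interpreted from the interval and not from significance. This needs saying in advance because interval and test can disagree near the threshold: at 2 v 9 events and 200 per arm the Newcombe interval (0.2 to 7.4 points) excludes zero while Fisher gives p = 0.062.

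In the test rule, insert the word expected before counts.

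The cost is one table column, a sentence on interpretation and one added word. No new data are needed. The intervals will be wide, so the conclusions on safety will have to be more cautious.

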	Mean change from baseline (95 % CI)	Mean change from baseline (95 % CI)	Treatment effect (95 % CI)	P-value
Below mean age				
Above mean age				
No diabetes				
Diabetes				
No hypertension				
Hypertension				
No statin therapy				
Statin therapy				
No renal failure				
Renal failure				
Baseline MGP <				
median				
Baseline MGP >= median				

Supplementary Table S2. Sensitivity analysis: Primary outcome and numerical secondary outcomes with imputation

If more than 5% of observations are missing at 24 months for the main analysis of the primary outcome reported in Table 2 the analysis will be repeated using multiple imputation (assuming missing at random) by mixed effects linear regression with all baseline characteristics included in Table 1 as covariates generating 100 imputations. Results will be reported in a table structured as Table 2.

	Vitamin K+D group	Placebo group			
	Mean change from	Mean change from	Treatment effect	p-value	
	baseline (95% CI)	baseline (95% CI)	(95% CI)		
Primary outcome: N	Primary outcome: Main analysis with imputation				
CAC score (all					
patients)					

Supplementary Table S3. Reasons of abandoning the study

	Vitamin K+D group (n=)	Placebo group (n=)
Excluded after inclusion		
Withdraw informed consent		
Significant comorbidity		
Lost interest		
Experienced side effect		
Personal reasons		
Died		

Figure 1. Enrollment and Randomization of Patients

[figure not shown]

Figure 2. CAC progression according to treatment allocation

CAC score at baseline, 12, and, 24 months will be presented in a graph, where the two treatment groups are plotted with their means and 95% confidence intervals (as obtained from the linear mixed models applied for Table 2). The figure will be presented for all patients (Figure 2A) as well as stratified by the baseline CAC score subgroups 400-999 (Figure 2B) and ≥1000 (Figure 2C). (See mockup figure 2A below, 2B and 2C are similar)

[figure not shown]

Figure 3. Change in plaque volume from baseline to 24 months

Change in plaque volume (mm³) with the 4 groups (total, calcified, noncalcified, low-attenuation noncalcified plaque) from baseline to 24 months follow-up will be presented as a box plot to show difference between the treatment group and placebo group.

[figure not shown]

Figure 4. Forest plot of stratified analyses of the primary outcome

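### Treatment effects are tested in 16 strata of 8 factors, but no between-stratum difference in effect is planned or reported

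*SAP*

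**What the plan says.** The SAP defines one model for the numerical outcomes, under Table 2. It has a treatment effect, "a fixed effect for time point (baseline, 12 and 24 months) and a fixed effects interaction between treatment and time point", a common baseline category for both arms and a random intercept per patient. It contains no subgroup term.

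That model is used in subgroups in two places:

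- **Table 2** has separate rows for men, women, baseline CAC 400-999 and baseline CAC ≥1000. Both factors are named secondary outcomes; the first reads "Change in CAC score from baseline to 24 months in men and women, respectively".
- **Supplementary Table S1** covers six more factors: age, diabetes, hypertension, renal failure, statin therapy and MGP. Its text opens with "Analyses of the primary outcome (progression in CAC score) will be repeated stratifying for age (below or above mean age at baseline") and goes on to list the other five. There, "The same models as for Table 2 will be applied for these analyses".

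In both shells each stratum row has its own "Treatment effect (95 % CI") column and its own p-value. For Figure 4, the text plans "Coefficients with 95% confidence intervals from stratified analyses (as reported in Supplementary table 1"); the mock-up is not available and is not used here. Under Statistical principles, "Two-sided p-values of 0.05 or less were considered to indicate statistical significance", with no exception for subgroup rows. The only interaction named anywhere in the SAP is treatment by time point.

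**The concern.** Two strata of one factor, printed one above the other with a p-value each, invite comparison. The usual shortcut is to read significant in one row and not in the other as a difference in effect. That is not a test of a difference. Each stratum has only part of the sample, so such a pair often arises when the effect is the same in both. The quantity that does address the question, the difference between the two stratum effects with its uncertainty, is the one the tables omit.

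At stake is the interpretation of two named secondary outcomes (sex and baseline CAC, the latter also shown in Figures 2B and 2C) and of six supplementary factors.

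**Working it through.** **Count.** Table 2: 2 factors × 2 = 4 strata. Table S1: 6 factors × 2 = 12 strata. Together 8 factors and 16 strata, each with a p-value.

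**Inputs from the SAP (Sample size considerations).** Effect 380 − 288 = 92 AU; SD 311 AU; 180 evaluable per arm; two-sided 5%; power 80%.

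**The SAP's own figure.** n per arm = 2 × 311² × (1.960 + 0.842)² / 92² = 179.4, so 180. Then 2 × 180 = 360, and 360 / 0.9 = 400. The stated sample size reproduces.

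**Assumptions.** Same effect and SD in every stratum, and stratum shares of 50/50, 25/75 and 15/85. The SAP fixes only the MGP split, at the median. Calculations use simple two-sample contrasts of change, not the full mixed model.

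**Chance of a discordant pair for one factor.** With n per arm in a stratum, s = 311 × √(2/n), and the power for a true effect d is p = Φ(d/s − 1.96) + Φ(−d/s − 1.96). The two strata hold different patients, so the chance that exactly one is significant is p₁(1 − p₂) + p₂(1 − p₁). At d = 92:

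| Split | n per arm | s (AU) | Power in each stratum | Exactly one significant |
|---|---|---|---|---|
| 50/50 | 90, 90 | 46.4, 46.4 | 0.510, 0.510 | 0.50 |
| 25/75 | 45, 135 | 65.6, 37.9 | 0.289, 0.681 | 0.58 |
| 15/85 | 27, 153 | 84.6, 35.6 | 0.192, 0.735 | 0.64 |

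The rate depends on the true effect:

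| Uniform effect (AU) | 0 | 46 | 92 | 138 | 184 |
|---|---|---|---|---|---|
| 50/50 | 10% | 28% | 50% | 26% | 4% |
| 25/75 | 10% | 29% | 58% | 45% | 20% |
| 15/85 | 10% | 30% | 64% | 62% | 42% |

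**At least one discordant factor among eight.** Simulated trials of 360 patients, with eight independent factors that all have the same split, and a uniform effect:

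- at 0 AU, about 35-39% of trials;
- at 92 AU, about 89-93%;
- at 184 AU, about 19% (50/50), 72% (25/75) or 96% (15/85).

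With even splits and 92 AU, the direct contrast was non-significant in about 90% of the discordant pairs.

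**What the direct contrast can deliver.** SE = 311 × √(2/n₁ + 2/n₂); half-width = 1.96 × SE; the difference detectable with 80% power = 2.80 × SE.

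| Split | SE (AU) | 95% CI half-width | Power for a 92 AU difference | Difference for 80% power |
|---|---|---|---|---|
| 50/50 | 66 | 129 | 29% | 184 |
| 25/75 | 76 | 148 | 23% | 212 |
| 15/85 | 92 | 180 | 17% | 257 |

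Each contrast has about a 5% false-positive rate. For eight independent tests, 1 − 0.95⁸ = 0.34.

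**The case against.** The best defence is that the SAP does what it sets out to do. The sex and baseline-CAC outcomes are defined as changes within subgroups, and Table S1 is described only as a repetition of the primary analysis by stratum. These are legitimate aims. Nowhere does the SAP say that effect modification will be inferred from stratum p-values. That stands: a reader might infer that the SAP plans such an inference, but the document does not say so.

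A reader might also infer that the planned output cannot show whether the effect differs. That goes too far. Each row carries an estimate and a 95% CI, and the strata of a factor are disjoint, so the difference and its SE can be worked out by hand. What holds is narrower: the SAP neither plans nor prints that comparison, while it does print a p-value beside every stratum.

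The third objection concerns the size. The eight-factor figures assume independent factors and one common split, and at 184 AU they swing from 19% to 96% with the split. Equal SD is doubtful for baseline CAC <1000 versus ≥1000, one of the two factors that are secondary outcomes. These points stand, so the aggregate figures illustrate the problem and do not forecast this trial. The per-factor figures do not need independence between factors.

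Finally, interaction tests here have little power. True, and a reason to report an estimate with a CI. It does not make paired p-values a better guide.

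**Conclusion.** The point holds as a weakness in how the subgroup results are to be reported. Sixteen stratum effects with p-values are planned across eight factors, with no between-stratum difference. If the effect is the design value of 92 AU in everyone, a given factor shows one significant and one non-significant stratum in about 50-64% of trials over the splits examined; with no effect, in about 10%. These figures rest on the SAP's SD and sample size, assumed splits (except the MGP median), and equal SD and equal effect across strata.

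The primary analysis and the sample size are untouched, and nothing here suggests that the stratum estimates should be dropped. The change is worth making because two of the factors are named secondary outcomes and the better quantity comes almost free.

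**What to change.** **Change.** For each of the eight factors, add to Table 2 and Table S1 (and to Figure 4 for its six factors) the 24-month between-stratum difference in treatment effect with its 95% CI and, if wanted, an interaction p-value. Keep the stratum estimates and CIs.

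- **Calculation.** Take the difference of the two planned stratum estimates, with SE = √(SE₁² + SE₂²).
- **Bootstrap.** The Table 2 provision resamples by "handling individual patients as bootstrapping clusters, and treatment groups as bootstrapping strata". If it is triggered in either stratum of a factor, bootstrap both and take the difference of the replicates.
- **Joint model, if preferred.** Apply the common-baseline constraint within each subgroup, with subgroup-specific means, time effects and variances.
- **Sentence to add.** *Any claim that the effect differs between subgroups rests on this difference and not on comparing stratum p-values; these contrasts are exploratory, not adjusted for multiplicity, and a non-significant contrast is not evidence of equal effects.*

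**Cost.** One column in two table shells, an addition to Figure 4 and one sentence. The first route needs no new model fits, apart from bootstrapping the second stratum when only one triggers it. The downside is low power, about 17-29% for a 92 AU difference, so most factors will probably end without evidence either way. If interaction p-values are printed, about one trial in three would show at least one false interaction among eight.
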